13.4.4.2 Descriptive System Categorical Analysis

For each EQ-5D-5L dimension the proportion of subjects reporting no, slight, moderate, severe, and extreme/unable to perform activity will be summarized descriptively at each timepoint using both OC and LOCF.

Change from Baseline in EQ-5D-5L health state will be assessed with the Pareto classification of health change (PCHC) method. Using this methodology, at Week 8/ET, each EQ-5D health state will be classified into one of four categories, relative to the Baseline health state:

- Improved = improved on at least one dimension and not worsened on any other dimension
- Mixed = improved on at least one dimension and worsened on at least one other dimension
- No change = no changes in any dimension
- Worsened = deterioration on at least one dimension and no improvement on any other dimension

The proportion of subjects in each PCHC category will be summarized descriptively at Week 8/ET using both OC and LOCF.

14 SAFETY ANALYSES

Safety variables include AEs, TEAEs, clinical laboratory variables, vital signs, body weight, BMI, physical examinations, electrocardiogram (ECG), C-SSRS, GCAS, MMSE, and ESRS-A variables. The safety summaries will be presented for the Safety Analysis Set using descriptive statistics. An MMRM model will be applied to the ESRS-A and MMSE total score endpoints. Safety variables will be summarized by treatment group.

14.1 Adverse Events

All Adverse events (AEs) will be coded using MedDRA version 20.0 or newer.

An AE will be considered a TEAE if it started on or after the first dose of study drug and no later than the last study drug dose date + 30. AEs reported on Day 1 based on pre-dose findings will not be considered as TEAEs.

For subjects enrolling in the long-term open-label study ACP-103-047, any AE started before the first dose of open-label study drug in Study ACP-103-047 will be considered as TEAE in Study ACP-103-046 but not in study ACP-103-047. Similarly, any AE reported after the first dose of open-label study drug in ACP-103-047 will be reported in association with the ACP-103-047 study only.

14.1.1 Primary Safety Analyses

TEAEs are the primary measure for this study. For the following summaries, the event counts and the number and percentage of subjects reporting TEAEs will be tabulated by treatment group:

- TEAEs by SOC and preferred term (PT)
- Most frequently reported TEAEs by SOC and PT
 - PTs reported by \geq 5% of subjects in either treatment group
- TEAEs by PT
- TEAEs by maximum severity, SOC, and PT
 - if more than 1 AE occurs with the same PT for the same subject, the subject will be counted only once for that PT using the most severe occurrence
- TEAEs related to study drug by SOC and PT
- Treatment-emergent serious adverse events (TESAEs) by SOC and PT
- TEAEs leading to study drug discontinuation or study termination by SOC and PT
- AEs with fatal outcome by SOC and PT
- TEAEs with fatal outcome (that occurred within 30 days of last dose) by SOC and PT

For tabulations that include SOC and PT the display will be sorted alphabetically by SOC and then by descending subject frequency for the PTs based on counts in the combined treatment groups within each SOC. SOCs will not be included in the TEAEs by PT tabulation. This display will be sorted by descending subject frequency based on counts in the combined treatment groups.

An AE listing by subject will display all events, including those which are not treatmentemergent, and will include the verbatim term in addition to the MedDRA SOC and PT. This listing will also include all relevant eCRF data associated with the event: e.g. date of onset, date resolved, date of the first and last dose of study drug, severity, frequency, outcome, relationship to study drug, action taken with study drug, and required therapy. When a date is presented, the study day associated with the date will also be displayed. Separate listings will be presented for subjects with SAEs, subjects with AEs leading to study drug discontinuation or study termination and subjects who died (if any). In these listings, an indicator for TEAEs will also be included.

14.1.2 Assessment of the Impact of COVID-19 on Adverse Events

The relationship of selected AEs to COVID-19 will be assessed by investigator as detailed in the DMP Appendix B, for those subjects who were not unblinded as part of the first interim analysis. Each of the primary safety analyses described in Section 14.1.1 will be additionally summarized by relationship to COVID-19 (Not related to COVID-19 vs. Related to COVID-19).

Both the Not related to COVID-19 and the Related to COVID-19 AE tables will be summarized using 2 sets of subjects: all subjects in the Safety analysis set, and subjects in the Safety analysis set that were not included in IA-1, as a proxy for pre- and post-COVID-19 analyses.

14.2 Secondary Safety Analyses

The secondary endpoints for this study are change from Baseline to Week 8 in ESRS-A, and change from Baseline to Week 8 in MMSE.

14.2.1 ESRS-A

The ESRS-A total score and the 4 individual global CGI-S scores will be summarized using descriptive statistics at Baseline and Weeks 1, 2, 4, 6, and 8/ET. The change from Baseline scores will also be summarized at Weeks 1, 2, 4, 6, and 8/ET.

The ESRS-A total score change from Baseline will be summarized using MMRM as specified in Section 13.2. The model will include categorical fixed effects for region, treatment group, visit, treatment-by-visit interaction, as well as the continuous fixed covariates for Baseline score and Baseline score-by-visit interaction. The MMRM results for the pimavanserin and placebo groups will be tabulated by visit.

The individual item scores will be listed but not summarized.

14.2.2 MMSE

The MMSE total score will be summarized using descriptive statistics at Baseline, Weeks 1, 2, 4, 6, and 8/ET. The change from Baseline scores will also be summarized at Weeks 1, 2, 4, 6, and 8/ET.

The MMSE total score change from Baseline will be summarized using MMRM as specified in Section 13.2. The model will include categorical fixed effects for region, treatment group, visit, treatment-by-visit interaction, as well as the continuous fixed covariates for Baseline

score and Baseline score-by-visit interaction. The MMRM results for the pimavanserin and placebo groups will be tabulated by visit.

The individual item scores will be listed but not summarized.

14.3 Other Safety Analyses

14.3.1 Clinical Laboratory Variables

Clinical laboratory tests are performed at Screening, Baseline, Week 4, and Week 8/ET visits. In general, laboratory test results are collected from a central laboratory

Due to COVID-19 disruptions it is possible that some test results may be collected from a local laboratory. A separate eCRF will capture local laboratory results in order to facilitate medical monitoring of subject safety. Local laboratory results will not be included in any summary data analysis; they will, however, be included in data listings, as well as a separate local laboratory PCI listing. All results (central and local) will be displayed in Système International [SI] units.

14.3.2 Chemistry

Clinical chemistry serum tests include the following:

- Sodium (Na), potassium (K), chloride (Cl), phosphorus (P), calcium (Ca carbon dioxide (CO₂), blood urea nitrogen (BUN), creatinine (CR), uric acid
 - Mg should only be performed at Screening
- Alaninine aminotransferase (ALT), aspartate aminotransferase (AST), gamma-glutamyl transpeptidase (GGT), alkaline phosphatase (ALP), total bilirubin (TBIL), lactate dehydrogenase (LDH)
- Glucose
- Albumin (ALB), total protein
- Prolactin
- Creatine kinase (CK)/creatine phosphokinase (CPK)
- Lipid panel
 - total cholesterol, HDL-cholesterol, triglycerides, LDL-cholesterol, cholesterol/HDL ratio, ratio, non-HDL-cholesterol, very low density lipoprotein cholesterol

- Magnesium (Mg), Vitamin B12, HbA1c, thyroid stimulating hormone (TSH) and reflex free T4 (if TSH is out of range)
 - these tests should only be performed at Screening
- Serum pregnancy test
 - performed only at Screening for women of childbearing potential

14.3.3 Hematology

Hematology tests include the following:

- Complete blood count (CBC) including:
 - White blood cell (WBC) count, absolute neutrophil count, complete differential (relative and absolute), hematocrit (Hct), hemoglobin (Hgb), red blood cells (RBC), platelets, reticulocyte count

14.3.4 Urinalysis

Urinalysis tests include the following:

- Blood, RBCs, WBCs, protein, glucose, ketones, specific gravity, pH
- A urine pregnancy test will be performed for all women of childbearing potential at Baseline and at each scheduled visit
 - If urine cannot be obtained in women of childbearing potential, a serum pregnancy test should be done in its place

14.3.5 Methods of Analysis for Clinical Laboratory Variables

14.3.5.1 Observed Values and Change from Baseline

Clinical laboratory values reported as continuous values for hematology, chemistry and urinalysis will be summarized using descriptive statistics at Baseline and scheduled post-Baseline visits. The change from Baseline values will also be summarized at scheduled post-Baseline visits.

The overall post-Baseline minimum and maximum observed and change from Baseline values will also be summarized. For urinalysis with categorical results, the number and percentage of subjects will be tabulated by category at Baseline and each scheduled post-Baseline visit. For the categorical urinalysis by-visit summary, the denominator is the number of subjects with non-missing values for the given parameter, visit, and treatment group.

For hemoglobin, hematocrit and uric acid, by-visit as well as overall post-Baseline minimum and maximum will be presented for each gender as well as for both genders combined.

14.3.5.2 Shift Tables

Laboratory values will be summarized in shift tables to determine the number and percentage of subjects with values classified as below (low), within (normal), or above (high) normal ranges at each scheduled post-Baseline visit relative to the same classification at the Baseline visit. For the by-visit shift summary, the denominator is the number of subjects with non-missing values at Baseline and the given visit for the given parameter and treatment group.

The shifts from Baseline to overall post-Baseline minimum and maximum will also be presented. The denominator is the number of subjects with non-missing Baseline and at least 1 post-Baseline value for the given parameter and treatment group.

For hemoglobin, hematocrit and uric acid, by-visit as well as overall post-Baseline minimum and maximum will be presented for each gender as well as for both genders combined.

14.3.5.3 Potentially Clinically Important (PCI) Laboratory Values

The number and percentage of subjects with PCI laboratory values at scheduled post-Baseline visits Week 4 and Week 8 and overall post-Baseline will be summarized by Baseline status (all or within normal range) for selected parameters. PCI criteria are listed in Table 3 and Table 4. Subjects with multiple PCI values for a given parameter will be counted only once for that parameter. All post-Baseline values will be considered, including unscheduled and out of window values

For the by-visit summary, the numerator for the percentage is the number of subjects with a post-Baseline PCI value for the given parameter, visit, and treatment group, and the denominator is the number of subjects with non-missing values for the given parameter, visit, and treatment group. For the overall post-Baseline summary, the numerator for the percentage is the number of subjects with at least 1 post-Baseline PCI value for the given parameter and treatment group, and the denominator is the number of subjects with at least 1 post-Baseline value for the given parameter and treatment group. For hemoglobin, hematocrit and uric acid, the count and percentage of subjects with PCI values will be presented for each gender as well as for both genders combined.

Table 3 Criteria for Potentially Clinically Important Laboratory Values – Hematology and Chemistry

Analyte	Conventional Unit	Low PCI Criteria	High PCI Criteria	SI Unit	Low PCI Criteria	High PCI Criteria	
	Hematology (whole blood)						
Hemoglobin (male)	g/dL	<11	>18	g/L	<110	>180	
Hemoglobin (female)	g/dL	<10	>17	g/L	<100	>170	
Hematocrit (male)	%	<30	>55	L/L	< 0.3	>0.55	
Hematocrit (female)	%	<30	>50	L/L	< 0.3	>0.5	
Leukocyte (White Blood Cell Count)	x 10 ³ /uL	≤2.8	≥15	x 10 ⁹ /L	≤2.8	≥15	
Neutrophils	x 10 ³ /uL	≤1.5	No upper limit	x 10 ⁹ /L	≤1.5	No upper limit	
Platelet Count	x 10 ³ /uL	≤75	≥700	10 ⁹ /L	≤75	≥700	
		Chemistry	(serum or plasma	1)			
ALT (SGPT)	U/L	No lower limit	≥3 X ULN	U/L	No lower limit	≥3 X ULN	
AST (SGOT)	U/L	No lower limit	≥3 X ULN	U/L	No lower limit	≥3 X ULN	
Total Bilirubin	mg/dL	No lower limit	≥1.5 ULN	umol/L	No lower limit	≥1.5 ULN	
BUN	mg/dL	No lower limit	≥30.0	mmol/L	No lower limit	≥10.71	
Creatine Kinase (CK)	U/L	No lower limit	≥3 ULN	U/L	No lower limit	≥3 ULN	
Sodium	mEq/L	≤125	≥155	mmol/L	≤125	≥155	
Potassium	mEq/L	≤3.0	≥5.5	mmol/L	≤3.0	≥5.5	
Calcium, total	mg/dL	<8.0	>11.0	mmol/L	<2.0	>2.75	
Lactate Dehydrogenase (LDH)	U/L	No lower limit	≥3 X ULN	U/L	No lower limit	≥3 X ULN	
Alkaline Phosphatase	U/L	No lower limit	≥3 X ULN	U/L	No lower limit	≥3 X ULN	
Uric acid (male)	mg/dL	No lower limit	≥10.5	umol/L	No lower limit	≥624.75	
Uric acid (female)	mg/dL	No lower limit	≥8.5	umol/L	No lower limit	≥505.75	
Albumin	g/dL	≤2.6	≥6.0	g/L	≤26	≥60	
Total Protein	g/dL	≤5.0	≥10.0	g/L	≤50	≥100	
Chloride	mEq/L	≤85	≥120	mmol/L	≤85	≥120	
Glucose (random)	mg/dL	≤45.1	≥200.0	mmol/L	≤2.48	≥11	
Serum Creatinine	mg/dL	Not Applicable	>1.5 ULN	umol/L	Not Applicable	>1.5 ULN	
Triglycerides	mg/dL	Not Applicable	>300	mmol/L	Not Applicable	>3.39	
Gamma-Glutamyl Transferase (GGT)	U/L	Not Applicable	≥3 ULN	U/L	Not Applicable	≥3 ULN	

 Table 4
 Criteria for Potentially Clinically Important Laboratory Values - Urinalysis

Urinalysis	Low PCI Criteria	High PCI Criteria
Blood (occult blood)	Not Applicable	≥Moderate
Protein	Not Applicable	≥100 mg/dL
Glucose	Not Applicable	≥500 mg/dL

14.3.5.4 Data Listings

All laboratory test results will be listed. The listings will include date and study day of collection. Out of range values will be flagged in the data listings (e.g., as 'L' or 'H'). Central and local laboratory values will be presented separately.

A listing of all PCI values will be provided. This listing will include all observations for those subjects and parameters for which at least one PCI value (including Baseline) was observed. Central and local laboratory PCI listings will be presented separately.

The pregnancy results (positive or negative) for female subjects of childbearing potential will be presented in a listing.

14.3.6 Vital Signs

Vital signs are assessed at Screening, Baseline, Weeks 1, 2, 4, 6 and Week 8/ET visits.

Due to COVID-19 disruptions it may be necessary for vital signs to be collected outside of the clinic by persons other than study site staff. These results will not be included in any summary data analysis; they will, however, be presented in data listings, and in a separate PCI listing of vitals measured by persons other than study site staff.

14.3.6.1 Vital Signs Variables

Vital signs include height (only measured at Screening), weight, derived BMI, systolic blood pressure (SBP), diastolic blood pressure (DBP), pulse rate, temperature, and respiratory rate.

14.3.6.2 Vital Signs Methods of Analysis

Vital signs will be summarized using descriptive statistics at Baseline and all scheduled post-Baseline visits. The change from Baseline values will also be summarized at the scheduled post-Baseline visits.

Vital sign values will be considered PCI if they meet the criteria listed in Table 4. The number and percentage of subjects with post-Baseline vital signs that are PCI will be summarized at scheduled post-Baseline visits and for overall post-Baseline. For the overall post-Baseline summaries, all post-Baseline values will be considered, including unscheduled and out of window values. Subjects with multiple PCI values for a given parameter will be counted only once for that parameter. For the by-visit summary, the numerator for the

percentage is the number of subjects with a post-Baseline PCI value for the given parameter, visit and treatment group, and the denominator is the number of subjects with non-missing values for the given parameter, visit and treatment group. For the overall post-Baseline summary, the numerator for the percentage is the number of subjects with at least 1 post-Baseline PCI value for the given parameter and treatment group, and the denominator is the number of subjects with at least 1 post-Baseline value for the given parameter and treatment group.

A listing of all PCI values will be provided (excluding those vitals collected by persons other than study site staff). There will be a separate PCI listing for vitals collected by persons other than study site staff. These listings will include all observations for those subjects and parameters for which at least one PCI value (including Baseline) was observed.

Table 5 Criteria for Potentiall	y Clinically Important `	Vital Signs
---------------------------------	--------------------------	-------------

		Criteria ^a			
Vital Sign Parameter	Unit	Observed Value	And/Or	Change Relative to Baseline	
Systolic blood pressure	mmHg	≥180	And	Increase of ≥20	
(supine or sitting)		≤90	And	Decrease of ≥20	
Diastolic blood pressure	mmHg	≥105	And	Increase of ≥15	
(supine or sitting)		≤50	And	Decrease of ≥15	
Dulgo (queino on gittino)	bpm	≥120	And	Increase of ≥15	
Pulse (supine or sitting)		≤50	And	Decrease of ≥15	
Weight	1	Not Applicable		Increase of ≥7%	
weight	kg			Decrease of ≥7%	

A post-baseline value is considered as a PCI value if it meets both criteria for observed value and change from baseline.

14.3.7 Electrocardiogram (ECG)

In countries outside of the Czech Republic, ECG is performed at Screening, Baseline, Week 2, and Week 8/ET. At the clinical sites in the Czech Republic, ECG is performed at all visits. For ECG data summaries, the common scheduled visits across all clinical sites will be used (i.e., Baseline, Week 2, and Week 8/ET).

All tracings will be evaluated by a central reading laboratory, including any collected outside of the clinic due to COVID-19 disruptions when possible. At the Baseline visit the machine-read results will also be recorded. ECG data summaries, including the cardiologist's interpretation, will be analyzed using the centrally evaluated data. All data, including the machine-read Baseline results, will be listed.

14.3.7.1 ECG Variables

ECG variables include heart rate, PR interval, RR interval, QRS interval, QT interval, and QTc intervals. QTc intervals include QTcB (Bazett's formula) and QTcF (Fridericia's formula). QTcF will also be categorized into the following categories (msec):

• Observed: ≤ 450 , 451 to 480, 481 to 500, and ≥ 500

• Change from Baseline: ≤ 10 , 11 to 30, 31 to 60, and ≥ 60

14.3.7.2 ECG Methods of Analysis

14.3.7.2.1 Observed Values and Change from Baseline

Observed values and the changes from Baseline of ECG variables will be summarized using descriptive statistics at Baseline and all scheduled post-Baseline visits. For the QTcF categorical analysis, the number and percentage of subject in each category will be summarized at each scheduled visit as well as overall post-Baseline maximum.

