1.3.1 Parkinson's Disease Psychosis Program

The scope of the development program for pimavanserin is the largest ever conducted in PDP. At the time of approval, 616 mostly older, late-stage PDP subjects had been evaluated in 16 countries over a span of >10 years. Clinically meaningful efficacy was established in Study ACP-103-020, a 6-week, placebo-controlled Phase 3 study (Cummings et al. 2014). This efficacy was supported by data from additional short-term Phase 2b/3 studies. In Study ACP-103-020, pimavanserin 34 mg consistently demonstrated statistically significant efficacy across multiple and independent endpoints, subject subgroups, and sensitivity analyses. Improvements in sleep and daytime wakefulness were also observed. These clinical benefits were achieved without worsening of Parkinson's disease motor symptoms and without a number of other safety concerns associated with atypical antipsychotics.

Pimavanserin is considered to be generally safe and well tolerated. Across all clinical studies of pimavanserin, the most frequently reported treatment-emergent adverse events (TEAEs) were in the central nervous system (CNS), gastrointestinal, and psychiatric systems. Most events were mild to moderate in intensity. The most common CNS TEAEs included dizziness (including postural), headache, and somnolence (drowsiness). Common gastrointestinal disturbances included dyspepsia, nausea, constipation, and vomiting. Severe nausea and vomiting were dose limiting in a few cases. Reported psychiatric conditions included agitation, insomnia, and confusional state.

Clinical and nonclinical safety pharmacology studies of pimavanserin suggest a potential risk for QT prolongation. The magnitude of effect in humans has been assessed in a thorough QT study with doses of pimavanserin ranging from 17 to 68 mg. In the Phase 3 PDP program, an average prolongation of approximately 5 to 8 ms was observed with pimavanserin 34 mg.

The US package insert for pimavanserin has a boxed warning that elderly patients with dementia-related psychosis treated with antipsychotic drugs are at an increased risk of death. Pimavanserin is not approved in the treatment of patients with dementia-related psychosis unrelated to the hallucinations and delusions associated with Parkinson's disease psychosis.

Additional information is provided in the pimavanserin Investigator's brochure and in the NUPLAZID® (pimavanserin) US package insert.

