Weight data was available for about half of the study participants at Day 85. Mean body weight and body mass index (BMI) remained relatively unchanged from Baseline to Day 85 in both treatment groups. Overall, 1 (1.8%) subject in the placebo group and 7 (14.6%) subjects in the pimavanserin group experienced weight decrease of \geq 7% and 5 (8.8%) subjects in the placebo group and 4 (8.3%) subjects in the pimavanserin group experienced weight increase of \geq 7%.

Changes from baseline in MMSE were similar in placebo and pimavanserin group indicating that pimavanserin did not affect cognitive function in these patients. Similarly, treatment with pimavanserin had no negative effect on motor function as measured by UPDRS Part III scores.

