4.3 Exclusion Criteria

A subject must not meet any of the following exclusion criteria to be eligible for the study:

- 1. Is in hospice, is receiving end-of-life palliative care, or is bedridden
- 2. Has neuropsychiatric symptoms that are primarily attributable to current delirium or substance abuse (i.e., neuropsychiatric symptoms not related to neurodegenerative disease)
- 3. Has current evidence of an unstable neurological, cardiovascular, respiratory, gastrointestinal, renal, hepatic, hematologic, or other medical disorder, including cancer or malignancies that, in the judgment of the Investigator, would jeopardize the safe participation of the subject in the study or significantly interfere with the conduct or interpretation of the study
- 4. Has a history of epilepsy

Final Version: 1.0 Date: 5 March 2021

- 5. Has atrial fibrillation unless adequately anticoagulated
- 6. Has a history of myocardial infarction, unstable angina, acute coronary syndrome, or cerebrovascular accident within the last 6 months prior to Visit 1 (Screening)
- 7. Has any of the following:
 - a. greater than New York Heart Association (NYHA) Class 2 congestive heart failure (Appendix J)
 - b. Grade 2 or greater angina pectoris (by Canadian Cardiovascular Society Angina Grading Scale) (Appendix K)
 - c. sustained ventricular tachycardia
 - d. ventricular fibrillation
 - e. torsades de pointes
 - f. syncope due to an arrhythmia
 - g. an implantable cardiac defibrillator
- 8. Has a history of human immunodeficiency virus (HIV) or hepatitis C infection
- 9. Has a history of neuroleptic malignant syndrome or serotonin syndrome
- 10. Has a known personal or family history of long QT syndrome or family history of sudden cardiac death
- 11. Has any of the following ECG results at Visit 1 (Screening) or Visit 2 (Baseline):
 - a. If the subject is **not** on citalogram, escitalogram, or venlafaxine:
 - i. QTcF >450 ms, if QRS duration <120 ms
 - ii. QTcF >470 ms, if QRS duration ≥120 ms
 - b. If the subject is on citalogram, escitalogram, or venlafaxine:
 - i. QTcF >425 ms, if QRS duration <120 ms
 - ii. QTcF >450 ms, if QRS duration \geq 120 ms

At Screening, if the set of triplicate ECGs has a prolonged QTcF due to an identifiable cause, and it is medically appropriate to address that cause, a repeat set of triplicate ECGs may be performed during Screening at the discretion of the Medical Monitor.

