2 OBJECTIVES

2.1 Primary Objective

The primary objective of this study is to assess the safety and tolerability of pimavanserin compared to placebo in adult and elderly subjects with neuropsychiatric symptoms related to neurodegenerative disease.

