3.3 Randomization

At Baseline (Visit 2/Week 0), eligible subjects who meet all inclusion criteria and do not meet any exclusion criteria will be randomized in a 1:1 ratio to receive either pimavanserin 34 mg or matched placebo, using an interactive response technology system. Randomization will be stratified by geographic region (North America, Europe, or rest of world).

The treatment assignments will be based on a pre-generated permuted-block randomization schedule. Blinding will be assured by restricting assess of Investigators and Sponsor personnel and/or designee to the treatment codes, and providing identical tablets and packaging for the pimavanserin and placebo treatments.

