3.5 Determination of Sample Size

Approximately 1500 subjects will be screened to enroll approximately 750 subjects, allowing for a 50% screen failure rate. Approximately 375 subjects will be randomized to the pimavanserin group as well as the placebo group (i.e., 375 subjects in each treatment group). With an assumed dropout rate of 30% in the double-blind phase, 525 subjects in total are expected to complete the study. In the event that the dropout rate is higher than anticipated, more subjects may be enrolled to ensure that at least 500 subjects complete the study.

A sample size of 375 subjects in each treatment group ensures that within each treatment group, the probability of observing at least 1 AE with a true incidence of 1.0% is 0.977; the probability of observing at least 1 AE with a true incidence of 1.5% is 0.997; and the probability of observing at least 1 AE with a true incidence of 2.0% is 0.999.

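### QTcF change and weight loss of at least 7%, both with figures in the protocol's background, are summarised by arm with no specified difference from placebo or confidence interval

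*SAP*

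**What the plan says.** The primary objective, in SAP 2.1 and Protocol 2.1, is to "assess the safety and tolerability of pimavanserin compared to placebo". SAP 3.3 states that subjects "will be randomized in a 1:1 ratio to receive either pimavanserin 34 mg or matched placebo", stratified by region.

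**ECG.** SAP 14.3.7.2.1 reads: "Observed values and the changes from Baseline of ECG variables will be summarized using descriptive statistics at Baseline and all scheduled post-Baseline visits". SAP 14.3.7.1 and 14.3.7.2.2 add QTcF categories and counts of potentially clinically important (PCI) values. The summary visits are Baseline, Week 2 and Week 8/ET.

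**Weight.** SAP 14.3.6.2 gives descriptive statistics, and: "The number and percentage of subjects with post-Baseline vital signs that are PCI will be summarized at scheduled post-Baseline visits and for overall post-Baseline". A gain or loss of at least 7% is one of the criteria in Table 5.

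**Where a difference from placebo is specified.** SAP 13.1 to 13.3 give LS mean differences with 95% CIs for CGI-S, CGI-I, SDI and EQ-5D-5L VAS. SAP 13.4.2.2 gives a region-weighted difference with a Newcombe interval for CGI-I response. SAP 14.2 applies the Section 13.2 model to ESRS-A and MMSE, and SAP 14 names no other safety variable for modelling.

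**Background.** Protocol 1.3.1 says that in the Phase 3 Parkinson's disease psychosis program "an average prolongation of approximately 5 to 8 ms was observed with pimavanserin 34 mg". Protocol 1.3.2 reports a mean QTc change of 9.4 ms in the pimavanserin arm of the Phase 2 Alzheimer's study, without a placebo mean. For weight, "7 (14.6%) subjects in the pimavanserin group experienced weight decrease of" at least 7%, against 1 (1.8%) on placebo.

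**The concern.** The objective is a contrast, and for these two outcomes the plan stops at the two columns. The order of priority also looks odd for a safety study: a sleep score and a proxy-rated health scale get a placebo-adjusted estimate with an interval, while QTcF does not.

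Both outcomes carry a number that this trial could check. The 9.4 ms Phase 2 figure shows the difficulty: quoted for one arm alone, it cannot be read as a drug effect.

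There is a secondary reason to prefer the between-arm figure for QTcF. Protocol 4.3 (criterion 11) excludes high QTcF at both Screening and Baseline; in the main case the limit is "QTcF >450 ms, if QRS duration <120 ms". Selecting on low readings lets later readings drift upward with no drug effect, so a within-arm change is not a clean measure of the drug.

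**Working it through.** **1. The plan's own design figure.** SAP 3.5 begins: "A sample size of 375 subjects in each treatment group ensures that within each treatment group, the probability of observing at least 1 AE". Using 1 − (1 − p)^375:
- p = 1.0%: 0.9769 (stated 0.977)
- p = 1.5%: 0.9965 (stated 0.997)
- p = 2.0%: 0.9995 (stated 0.999)

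Completers are 750 × 0.70 = 525, about 262 per arm. All of these reproduce. No figure is stated for QTcF or weight.

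**2. Phase 2 weight loss.** The denominators are not given, but the percentages imply them. 7/48 = 14.58%, and 4/48 = 8.33% matches the reported 8.3% with weight gain. 1/57 = 1.75%, and 5/57 = 8.77% matches the reported 8.8%.
- Difference: 14.58 − 1.75 = 12.8 points
- Newcombe 95% CI: 2.3 to 25.5 points

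The signal is suggestive and imprecise. It is also one outcome picked from several.

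**3. Precision available for QTcF.** Half-width = 1.96 × SD × √(2/n). The SD of change is not in the documents; 12 to 25 ms is assumed.

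| SD of change (ms) | n = 375 per arm | n = 262 per arm |
|---|---|---|
| 12 | 1.7 | 2.1 |
| 15 | 2.1 | 2.6 |
| 20 | 2.9 | 3.4 |
| 25 | 3.6 | 4.3 |

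Against a background effect of 5 to 8 ms, all of these are informative.

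**4. Gain from adjusting for Baseline QTcF.** Let ρ be the correlation between Baseline and later QTcF. Ignoring truncation, the unadjusted variance of change is 2σ²(1 − ρ) and the adjusted variance is σ²(1 − ρ²), so the reduction is (1 − ρ)/2. A reduction of 10 to 15% corresponds to ρ of 0.80 to 0.70. It narrows the interval by 1 − √0.90 = 5% to 1 − √0.85 = 8%. A lower ρ would give somewhat more.

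**5. Precision available for weight loss.** Half-width ≈ 1.96 × √[(p₁(1 − p₁) + p₂(1 − p₂))/n]. The assumed n is 350 per arm, between 262 completers and 375 randomised.
- Phase 2 rates, 14.6% versus 1.8%: 1.96 × √[(0.1247 + 0.0177)/350] = 4.0 points
- Lower rates, 5% versus 2% (assumed): 1.96 × √[(0.0475 + 0.0196)/350] = 2.7 points

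**6. Drift from the QTcF entry limits.** This was simulated with zero drug effect, a triplicate mean at Screening, a single tracing at Baseline, and the same limit applied at both. All of the following are assumed: unselected mean 410 to 430 ms, total SD 20 to 25 ms, visit-to-visit SD 8 to 16 ms.
- 450 ms limit: +0.1 to +3.2 ms; +0.8 ms at mean 420, SD 20, visit SD 12
- 425 ms limit (subjects on one of three named antidepressants): +0.7 to +9.8 ms; +3.2 ms in the same central case

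The real cut is less sharp. Protocol 6.3.4 allows enrolment on the local machine read at Baseline, while SAP 14.3.7 analyses the central read.

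**The case against.** Descriptive safety reporting is a declared choice. Protocol 9.2 plans no formal testing of safety hypotheses, and ECG and weight belong to no endpoint tier, whereas ESRS-A and MMSE are secondary endpoints. QT is covered by categorical summaries by arm, and Protocol 1.3.1 says its magnitude was assessed in a thorough QT study. Even TEAEs, the primary measure, have no between-arm estimate. All of this is true, and it limits the point to an improvement. It does not answer it fully: SAP 1 and 19 have already departed from the descriptive position for other endpoints, and an interval without a test does not conflict with Protocol 9.2.

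A reader might infer more than the documents support, in four ways.
- **That the plan leaves no measure of precision.** It does not. SAP 5.1 tabulates n, mean, SE and SD for each arm, so a crude QTcF difference and its SE, √(SE₁² + SE₂²), can be derived. The weight table already gives numerators and denominators by arm.
- **That the entry limits bias the comparison.** They act before randomisation, so the expected drift is the same in both arms; it shows in the placebo column and cancels in the difference. Nothing in the documents presents a within-arm change as a drug effect.
- **That Baseline QTcF is a strong predictor of change.** At 10 to 15% of the variance it is a moderate one.
- **That these are the only risks in the background.** Protocol 1.3.1 also cites a boxed warning on death, and 1.3.2 reports more SAEs (16.7% versus 11.0%) and more agitation. For weight, 1.3.2 adds that data were available for about half of participants and that mean weight was relatively unchanged.

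**Conclusion.** The point holds as a gap in specification. QTcF change and weight loss of at least 7% are two measured outcomes with figures in the protocol's own background. The plan specifies no pimavanserin-minus-placebo estimate or interval for either, although its objective is comparative and it provides such estimates elsewhere. A reader can build a crude difference, but it would be neither prespecified nor adjusted for Baseline QTcF or the region stratum.

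The trial is large enough for both estimates to be useful: a half-width of about 1.7 to 4.3 ms for QTcF, and about 3 to 4 percentage points for weight loss. These figures rest on assumed SDs, event rates and numbers evaluable, because the documents give none. The entry-limit drift is a supporting reason only: roughly 0 to 3 ms under the 450 ms limit, and more under the 425 ms limit, on assumed SDs.

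No planned result is invalid. This is a cheap improvement.

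**What to change.** Add two displays on the Safety Analysis Set.

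1. **QTcF change at Week 2 and Week 8**, from the Section 13.2 MMRM or an ANCOVA with treatment, region and Baseline QTcF. Report the LS mean difference from placebo with its 95% CI and no p-value. Use the central read, as SAP 14.3.7 already does.
2. **Weight decrease of at least 7% at any post-Baseline visit.** Report the risk difference with Cochran-Mantel-Haenszel weights by region and a Newcombe 95% CI, the method in SAP 13.4.2.2. Keep the overall post-Baseline denominator of SAP 14.3.6.2, and keep the SAP 14.3.6 rule that leaves readings taken by non-site staff out of summaries.

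The cost is two tables, from data already collected and methods already in the SAP, with no extra subjects or visits. The downside is two more estimates without multiplicity control. Showing intervals only, labelled as estimation, keeps them within the no-testing position of Protocol 9.2.
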